2.4.5.2 Analysis of hypoglycemia

Treatment-emergent hypoglycemia events will be tabulated separately from the AEs.

Event frequency and incidence of hypoglycemia events will be summarized by treatment for all reported hypoglycemia and per type of hypoglycemic event described in [Section 2.1.4.5](#) (ie, severe, documented symptomatic, asymptomatic, probable symptomatic, relative) for safety population. Incidence of severe or documented symptomatic hypoglycemia events will be summarized by study period (≤ 4 weeks (titration period), >4 weeks to ≤ 8 weeks, >8 weeks to ≤ 30 weeks, >30 weeks) and according to time of occurrence (nocturnal [ie, 00:00 to 05:59 am], daytime [ie, 06:00 am to 23:59]) for safety population. Documented hypoglycemia (symptomatic or asymptomatic) will be also evaluated for the more stringent plasma glucose threshold of <54 mg/dL (3.0 mmol/L), as well as for ≥ 3.0 and <3.9 mmol/L (≥ 54 and <70 mg/dL). Frequency and percentage of participants with at least one hypoglycemia event will be summarized as well.

Event rate of hypoglycemia per participant year will be calculated by treatment using the total number of hypoglycemia events from all participants (denoted as n) divided by the total exposures from all participants expressed in years (ie, participant exposure in days divided by 365.25, denoted as t). Multiple events from an individual participant will all count. Event rates of hypoglycemia per participant year (all reported hypoglycemia, severe, documented symptomatic, asymptomatic, probable symptomatic, relative hypoglycemia, and documented hypoglycemia with plasma glucose <54 mg/dL [3.0 mmol/L]) will be presented by treatment group for the 30-week core on-treatment period and the whole on-treatment period.

The summary of frequency and event rate in participant years for severe or documented symptomatic hypoglycemia will be provided as appropriate by gender (Male, Female), age group (<50 , ≥ 50 to <65 , ≥ 65 to <75 , ≥ 75 years), and race (Asian, Black or African American, White, Other).

A KM curve will also be provided by treatment group for the time to first severe or documented symptomatic hypoglycemia during the whole on-treatment period.

A listing of participants for all severe or documented symptomatic hypoglycemia events reported on the specific eCRF “Hypoglycemic Event Information” page will be provided and sorted by participants.

2.4.5.3 Deaths

The following summaries of deaths will be generated:

- TEAE leading to death (death as an outcome on the AE case report form page as reported by the Investigator) during whole on-treatment period by primary SOC, HLT, and PT showing number (%) of participants (Safety population)
- AE leading to death (death as an outcome on the AE case report form page as reported by the Investigator) during whole 30-week on-study observation period by primary SOC, HLT, and PT showing number (%) of participants (Safety population)
- Number (%) of participants who died by study period (on-study, on-treatment, post-study) (Safety population)
- Pre-treatment AEs, TEAEs and post-treatment AEs leading to death (death as an outcome on the AE case report form page as reported by the Investigator) by study period

(pre-treatment period, on-treatment period, and post-treatment period) showing number (%) of participants

- Listing of all Deaths (Screened participants)

2.4.5.4 Product complaints

All product complaint summaries during the on-treatment period will be generated in the safety population with number (%) of participants experiencing at least one event as well as number of events and rate per participant-years.

Rate per participant-years will be defined as the number of events divided by the cumulative duration of participants' exposure expressed in years.

The overview of product complaints with the details below will be generated:

- Any product complaint
- Any product complaint related to AEs

In addition, the analysis below will be conducted.

- Any product complaint categorized by type of complaint
- AE(s) leading to product complaints by primary SOC and PT
- Listing of all product complaints

2.4.5.5 Analyses of laboratory variables

All hematology and clinical chemistry results will be listed by treatment group, participants and visit, including scheduled and unscheduled/repeat measurements.

The summary statistics (including number, mean, median, standard deviation, minimum and maximum) of all protocol-required laboratory variables (central laboratory values and changes from Baseline) will be calculated for each scheduled visit and last value on treatment by treatment group.

The incidence of PCSAs at any time during the whole on-treatment period will be summarized by biological function and treatment group whatever the Baseline level and/or according to the following Baseline status categories:

- Normal/missing
- Abnormal according to PCSA criterion or criteria

For parameters for which no PCSA criteria are defined, similar table(s) using the normal range will be provided. For calcitonin, no PCSA criterion is defined. Similar summaries will be provided using the pre-defined categories: \leq ULN, $>$ ULN - $<$ 20 ng/L, \geq 20 - $<$ 50 ng/L, and \geq 50 ng/L (Note that ng/L is the standard international unit and is equivalent to pg/mL).

All measurements collected during the whole on-treatment period, including values from unscheduled visits, will be considered for the PCSA summaries. These summaries will include participants in the safety population who have at least 1 assessment performed during the whole on-treatment period. When a PCSA definition involves only a change from baseline value, participants must also have a baseline value to be included in the summaries, and when required by the definition of the abnormality, participants must also have available laboratory normal ranges.

For some parameters, such as liver enzymes, the lower limit of normal (LLN) is not considered clinically relevant, and values below this limit are considered normal. When there are multiple PCSA criteria for a specific parameter (eg, ALT), the participant will be counted once during the whole on-treatment period for the specific parameter in question under the worst/maximum PCSA category.

Elevated liver parameters will be summarized by treatment group in safety population.

For PCSA, both central and local lab data will be used.

A listing of participants with at least 1 post-baseline PCSA (or out of normal range when no PCSA criterion is defined) will be provided and will display the entire participants' profile across time for all parameters belonging to the corresponding biological function. Individual data listings will include flags when applicable:

- Baseline values will be flagged “B”.
- Normal laboratory ranges, available for most laboratory parameters, will be identified as ULN and LLN. Baseline, and individual data will be flagged “L” if the value is below the LLN and will be flagged “H” if it is above the ULN.
- Laboratory PCSA criteria will be used for the corresponding laboratory parameters. Values reaching a PCSA limit will be flagged (+, ++, -, or – depending upon the direction and level of the abnormality). Flags for WBC and differential counts will be determined using data expressed in international units.

For parameters whose PCSA criteria are multiples of the ULN, the parameter's value will also be expressed as a multiple of the ULN in the individual data provided.

2.4.5.6 Analyses of vital sign variables

The summary statistics (including number, mean, median, standard deviation, minimum and maximum) of all vital sign variables will be calculated for each scheduled visit by treatment group.

The incidence of PCSAs at any time during the whole on-treatment period will be summarized by treatment group irrespective of the Baseline level and/or according to the following Baseline status categories:

- Normal/missing,
- Abnormal according to PCSA criterion or criteria.

A listing of participants with at least 1 post-baseline PCSA will be provided and will display the participant's profile over time of all vital sign parameters. Individual data listings will include the following flags:

- Baseline values will be flagged "B",
- Parameter values reaching a PCSA limit will be flagged (+, or - depending of the direction).

2.4.5.7 Analyses of electrocardiogram variables

The frequency and percentage of 12-lead ECG interpretation (normal, abnormal) will be provided at each scheduled visit by treatment group.

2.4.5.8 24-hours Holter ECG

The summary statistics (including number, mean, median, standard deviation, minimum and maximum) of Holter ECG variables (24-hour mean heart rate and night-time mean heart rate, and changes from baseline) will be calculated for each applicable visit by treatment group and overall.

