ECG & Holter data	
The incidence of potentially clinically significant abnormalities (PCSA), defined as abnormal values considered medically important by the Sponsor according to predefined criteria/thresholds based on literature review, will be summarized at any time during the 30-week core on-treatment period and during the whole on-treatment period.
 
Results will be presented both in standard international and conventional US units
 
The incidence of Normal and Abnormal ECG status at any time during on-treatment period will be summarized by treatment group whatever the Baseline level and according to Baseline status.
 
Tables will be presented on the “30-week main on-treatment period” and on the “whole on-treatment period including the 26-week controlled Treatment Extension Period”

Exploratory	Will be described in the statistical analysis plan finalized before database lock

AE adverse event; ECG electrocardiogram; HLGT higher-level grouped term; HLT higher-level term; LLT lower-level term; MedDRA Medical Dictionary for Regulatory Activities; PCSA potentially clinically significant abnormalities; PT preferred term; SAE serious adverse event; SOC system organ class; TEAE treatment-emergent adverse event.

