2.1.4.2 Laboratory safety variables

Clinical laboratory data consists of blood analysis, including hematology, clinical chemistry and urinalysis. Clinical laboratory values will be summarized in both standard international units and conventional units (US) when applicable.

Blood samples for clinical laboratories will be collected at designated visits (see Schedule of Activities in [Appendix C](#)). The following laboratory parameters will be measured at central laboratory:

- Hematology
 - Red blood cells and platelets: Platelet count, Red blood cell count, Hemoglobin, Hematocrit;
 - White blood cells: White blood cell count, differential count (Neutrophils, Lymphocytes, Monocytes, Eosinophils, Basophils).
- Clinical chemistry
 - Pancreatic enzymes: Amylase, Lipase;

- Electrolytes: Potassium, Sodium;
- Renal function: Creatinine, Estimated glomerular filtration rate (MDRD formula);
- Liver function: Alanine aminotransferase (ALT), Aspartate aminotransferase (AST), Alkaline phosphatase (ALP), Total bilirubin;
- Lipid profile:
 - Triglyceride, Total cholesterol, Low-density lipoprotein cholesterol, High-density lipoprotein cholesterol;

For triglycerides, only values assessed in fasted participants will be analyzed.

- Calcitonin.

Technical formulas are described in [Section 2.5.1](#).

2.1.4.3 *Vital signs variables*

Vital signs include: sitting heart rate (bpm), as well as sitting systolic and diastolic blood pressures (mmHg).

2.1.4.4 *Electrocardiogram variables*

ECG variables include 12-lead ECG interpretation (normal/abnormal) provided by the investigator, 24-hour mean heart rate (bpm) and night-time mean heart rate (bpm) provided by reading center. 12-lead ECG recording will be performed locally at Randomization, Week 12, Week 30 and Week 56. Investigator's interpretation of normal and abnormal will be reported in the eCRF.

24-hour Holter ECGs will be recorded automatically by the device and will be sent to an ECG reading center for further analysis. A minimum of 19 hours (80%) of evaluable data are needed for analysis of the 24-hour ECG record.

2.1.4.5 *Hypoglycemia*

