2.5.5 Unscheduled visits

Unscheduled visit measurements of laboratory data, vital signs, and ECG will not be included in the by-visit summaries but will be used for computation of Baseline and PCSAs.

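### SAP 2.4.5.7 replaces the protocol's any-time 12-lead ECG incidence by baseline status with by-visit percentages, and the SAP change table does not record it

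*SAP*

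**What the plan says.** Protocol Table 6, in the row on ECG and Holter data, states: "The incidence of Normal and Abnormal ECG status at any time during on-treatment period will be summarized", and this is to be done "by treatment group whatever the Baseline level and according to Baseline status". The same row asks for tables on the 30-week and the whole on-treatment periods.

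SAP 2.4.5.7 consists of a single sentence on the 12-lead ECG: "The frequency and percentage of 12-lead ECG interpretation (normal, abnormal) will be provided at each scheduled visit by treatment group". It contains no any-time count, no split by baseline status and no table of potentially clinically significant abnormalities (PCSAs).

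Two other SAP sections decide where the remaining readings go:

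- SAP 2.1.4.4 defines what is analysed: "ECG variables include 12-lead ECG interpretation (normal/abnormal) provided by the investigator". The other ECG variables listed there are the 24-hour and night-time mean heart rates from the reading center. The 12-lead recordings are scheduled at randomization and at Weeks 12, 30 and 56.
- SAP 2.5.5 deals with readings off the schedule: "Unscheduled visit measurements of laboratory data, vital signs, and ECG will not be included in the by-visit summaries". Their only remaining use under that section is in deriving baseline values and PCSAs.

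**The concern.** The protocol's table asks how many participants had an abnormal ECG at some point on treatment, given how they started. The SAP's table asks what share of tracings was abnormal at each of a few visits. The second does not answer the first, because a participant who was abnormal before dosing and one who became abnormal on treatment add equally to the percentage.

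Unscheduled tracings raise a related problem. The protocol generates 12-lead ECGs away from the nominal visits. Protocol 8.2.3.1 asks for a recheck of any new abnormality. Protocol 6.1.2.1 calls for an unscheduled pre-rescue visit with the end-of-treatment assessments, from which the Holter recording and the 7-point profile are exempted but the 12-lead ECG is not. An abnormality seen only on such a tracing is outside the by-visit table.

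At stake is the completeness of a descriptive safety display that the sponsor planned in the protocol.

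**Working it through.** No figure in the plan needs reproducing here, so the check compares the texts and adds one identity.

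**1. Protocol against SAP**

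| Feature | Protocol Table 6 | SAP 2.4.5.7 |
|---|---|---|
| Unit counted | Participants, by status at any time on treatment | Readings at each scheduled visit |
| Baseline split | Overall and by baseline status | None |
| Unscheduled ECGs | Not excluded | Excluded from by-visit summaries by SAP 2.5.5 |
| Periods | 30-week and whole on-treatment | Not stated there; the opening of SAP 2.4.5 applies both to safety results generally |

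**2. Is the change recorded?** SAP 1.6 presents Table 2 as the history of major statistical changes. Version 3 itemises removals, including the control-based imputation sensitivity analysis, the ANCOVA for mean 24-hour self-monitored glucose and the Cox model for time to rescue. Neither version 2 nor version 3 mentions the ECG analysis.

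**3. Is it a general simplification?** No. SAP 2.4.5.5 (laboratory) and 2.4.5.6 (vital signs) both keep any-time on-treatment incidence of PCSAs, with baseline categories of normal/missing and abnormal. Only the ECG section lost this form, and no reason is given.

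**4. What the by-visit table can identify.** Take one arm of n participants with ECGs at baseline and at visit v. Let B be the number abnormal at baseline, A the number abnormal at visit v, N the number newly abnormal at v (normal at baseline), and R the number abnormal at baseline but normal at v. Then

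A − B = N − R.

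The table shows A and B, hence only the net change. Because R cannot be negative, and N cannot exceed either A or n − B,

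max(0, A − B) ≤ N ≤ min(A, n − B).

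If the percentage does not move (A = B), the lower limit is 0, while the upper limit is above 0 whenever some but not all participants were abnormal at baseline. The number newly abnormal at any of the three post-baseline visits is less determined still, since the table does not show whether the same people are abnormal at each visit.

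**5. Where an unscheduled abnormal reading goes.** SAP 2.5.5 removes it from the by-visit summary and sends it to Baseline and PCSA computation. The general PCSA rule in SAP 2.4.5 names ECG and counts nonscheduled evaluations. However, the ECG criteria in Appendix B are all numeric (heart rate, PR, QRS, QT, QTc), and none is met by a reading of abnormal. The only 12-lead variable in SAP 2.1.4.4 is that reading, and SAP 2.4.5.7 plans no PCSA table. As written, an on-treatment unscheduled abnormal reading reaches no planned summary of ECG interpretation.

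**The case against.** The other side has a good deal to say, and much of it stands.

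- **Adverse event tables.** Under Protocol 8.2.3.1 a new abnormality judged clinically significant is reported as an adverse event, so it can appear in the treatment-emergent tables of SAP 2.4.5.1. A reader might infer that unscheduled abnormal ECGs vanish from the report altogether. The documents do not support that: besides this route, SAP 2.4.5 and 2.5.5 nominally send such ECGs to the PCSA counts.
- **Side-by-side reading.** Baseline and later percentages can be compared within randomized arms, so a net rise would show. A reader might infer that new abnormalities cannot be seen at all. What is actually lost is the participant-level shift, where new and resolved cases offset each other.
- **Rechecks.** If the abnormality was found at a scheduled visit, that reading is already in the table, and the omitted recheck is only a confirmation. The documents do not say how frequent unscheduled ECGs are.
- **Computability.** That the numeric criteria lack input is inferred from the variable list in SAP 2.1.4.4. The e-CRF is not available, so it cannot be asserted that no intervals were recorded.
- **Periods.** The opening of SAP 2.4.5 already presents safety results on both on-treatment periods, so two-period reporting has not plainly been abandoned.
- **Importance.** The 12-lead ECG is not an endpoint in Protocol Table 1, and the Amendment 03 rationale leaves its descriptive presentation to the SAP. The cardiac effect named in Protocol 2.3 is increased heart rate, which is covered by Holter change from baseline (SAP 2.4.5.8) and vital-sign PCSAs by baseline status (SAP 2.4.5.6).

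These points limit the consequence. They do not explain why a table specified in the protocol was replaced by one that answers a different question.

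**Conclusion.** The point holds as a minor one. SAP 2.4.5.7 departs from Protocol Table 6 without a record of the change. The substitute cannot separate new from pre-existing abnormal readings at participant level, and unscheduled ECGs enter no planned summary of interpretation. The loss mainly concerns abnormalities not reported as adverse events. No primary or key secondary conclusion is affected.

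No numerical size is attached. Neither document gives a baseline rate of abnormal ECGs or a count of unscheduled tracings, and safety analysis is essentially descriptive under SAP 2.4.5, so a precision argument built on an assumed rate would prove little. The conclusion rests on the two texts as written and on SAP 2.1.4.4 being a full list of the 12-lead variables to be analysed. If intervals were collected and a PCSA table was intended, the remark about unscheduled ECGs would weaken, but the missing any-time incidence by baseline status would remain.

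**What to change.** In SAP 2.4.5.7, restore the number and percentage of participants with at least one abnormal 12-lead ECG at any time on treatment, from scheduled or unscheduled recordings. Present it by treatment group, overall and by baseline status (normal or missing / abnormal), for the 30-week core and the whole on-treatment periods. Keep the by-visit table as supportive.

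If the sponsor prefers to drop the any-time table, record the removal and its reason in SAP Table 2. In either case, state in SAP 2.4.5.7 whether an ECG PCSA table is planned and from which collected variables.

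The cost is one descriptive table from data already collected, in the format that the SAP already uses for vital signs.

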2.4.5.9 Analyses of other safety endpoints

Anti-drug Antibody

An anti-drug antibody positive participant is defined as a participant with at least one treatment-induced or treatment-boosted ADA-positive sample at any time.

Summaries of ADA data will be provided for participants treated with efpeglenatide only. All summaries related to kinetics of ADA response (ADA status and magnitude, ADA attributes, participant status, ADA incidence) will be descriptive; no statistical significance tests will be performed on ADA data. The incidence of ADA status (positive/negative/inconclusive) will be summarized by visit, treatment, and individual titer for the ADA population. Incidence of treatment induced and treatment-boosted (treatment emergent) ADA during on-study period will be summarized by treatment. Incidence of participants with ADA cross-reactivity to endogenous GLP-1 (positive/negative), and to endogenous glucagon (positive/negative) will be summarized by visit and treatment. Incidence of participants with ADA directed against PEG linker, HMC001 moiety and exendin-4 moiety (positive/negative), will be summarized by visit and treatment.

Incidence of participants with neutralizing antibodies against efpeglenatide and against endogenous GLP-1 and Glucagon will be summarized by visit and treatment.

ADA data from unscheduled visits (due to SAE for example) will not be included in summary and will be presented only in ADA values listing.

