2.3.3 ADA population

ADA population is defined as:

- All participants from the safety population with at least 1 post-Baseline valid ADA sample after drug administration.

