- The frequency of TEAEs over time will be provided for nausea, vomiting, and diarrhea, using weekly time intervals through Week 8 and then every 4 weeks through Week 56, ie, [0-1] week, [1-2] weeks, [2-3] weeks, [3-4] weeks, etc. In each time interval, the numerator in the calculation of percentages will be the number of participants with at least 1 TEAE occurring in this time interval. Two types of analyses will be included: (1) only

the first event will be counted for each participant and all recurrent events will not be included, and the denominator for the calculation of percentages will be the number of participants at risk at the beginning of the time interval who did not experience a first event in the preceding intervals; and (2) the recurrent events in subsequent intervals will be counted once for each participant in the numerator of the corresponding interval, and the denominator for the calculation of percentages will be the number of participants at risk at the beginning of the time interval. A histogram of the frequency over time (by weekly intervals) will also be presented as appropriate.

- All TEAEs by BMI subgroup (< 30, \geq 30 kg/m²)
- All TEAEs by Anti-Efpeglenatide Antibody Status (Positive, Negative)

Analysis of all treatment emergent serious adverse event(s)

- All serious TEAEs by primary SOC, HLGT, HLT, and PT, showing the number (%) of participants with at least 1 serious TEAE

All serious TEAEs related to IMP, by primary SOC and PT, showing the number (%) of participants with at least 1 serious TEAE.

Analysis of all treatment-emergent adverse event(s) leading to treatment discontinuation

All TEAEs leading to treatment discontinuation, by primary SOC, HLGT, HLT, and PT, showing the number (%) of participants

Analysis of adverse events of special interest and adverse events requiring specific monitoring

Adverse events of special interest (AESI) and adverse events requiring specific monitoring (AERSM) include AE defined in [Section 2.1.4](#) and the criteria of AESI and AERSM are in [Table 3](#).

Table 3 - Criteria for AESI and AERSM

AE Grouping	Criteria
AESI	
Pregnancy	“Pregnancy” or “Partner pregnancy” checked
Symptomatic Overdose	“Overdose” checked and symptomatic (AEOVSYMP) = “Yes”
Increase in ALT >3 ULN	“ALT Increase” checked and Yes to the question “Is the event an AESI?” in eCRF form “Adverse Events”
AERSM	
Severe GI event	AE severity = “severe” using Gastrointestinal disorders CMQ

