The scheduled measurements at the endpoint visit (Week 30 or Week 56) as collected will be used in the efficacy analyses including those obtained after IMP discontinuation and/or introduction of rescue therapy. For participants whose efficacy measurement is not available at the endpoint visit, the measurement at unscheduled visit (including the end of treatment and/or study visit for those prematurely discontinued) will be used if the unscheduled measurement is within +/-30 days (7 days for FPG and SMPG) of the date of the end point visit [targeted study Day 210 for Week 30 (or Day 392 for Week 56)]. If multiple measurements are associated to the same targeted date, the closest to the targeted study day will be used. In case of equality, the last measurement will be used. If there are still no measurement for a given parameter at an endpoint visit, the data is considered missing for efficacy analyses, where multiple imputation would be applied as appropriately as described in [Section 2.4.4.1](#).

Linked adverse events that worsened or became serious

An AE that worsened or became serious will have a separate record in the data from the original event record with a reference identification number that links the new record to the original record. An AE that worsened or became serious will be considered a new recurring AE in the summary of recurrent events or in the summary of events by time intervals.

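### SAP 2.4.5.9 contradicts itself on whether anti-drug antibody samples from unscheduled visits count toward a participant's ADA status

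*SAP*

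**What the plan says.** SAP 2.4.5.9 opens by defining an ADA-positive participant as one with "at least one treatment-induced or treatment-boosted ADA-positive sample at any time". It plans a participant-level table: "Incidence of treatment induced and treatment-boosted (treatment emergent) ADA during on-study period will be summarized by treatment". It closes with the exclusion: "ADA data from unscheduled visits (due to SAE for example) will not be included in summary and will be presented only in ADA values listing".

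Other places that bear on the point:

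- SAP 2.3.3 defines the ADA population as "All participants from the safety population with at least 1 post-Baseline valid ADA sample after drug administration". Samples need not come from scheduled visits.
- SAP 2.4.5.1 tabulates all TEAEs by antibody status, and SAP 2.4.4.1 describes Week 30 HbA1c change by treatment-emergent ADA status.
- SAP 2.1.5.1 sorts responders into persistent, transient and indeterminate classes from the pattern of positive samples.
- SAP 2.5.5 deals with unscheduled laboratory, vital-sign and ECG values differently: they "will not be included in the by-visit summaries but will be used for computation of Baseline and PCSAs".
- Protocol Table 1 counts participants with treatment-induced and treatment-boosted ADA over the study and makes no exception for unscheduled samples.
- Protocol 6.1.2.1 requires an expressly unscheduled visit before rescue therapy, with the end-of-treatment assessments apart from the 7-point SMPG and the 24-hour ECG. The schedule of activities (protocol 1.3) places ADA sampling at the end-of-treatment visit, so a sample is due at the pre-rescue visit too.

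**The concern.** The exclusion carries no by-visit limit, and the word *only* leaves these samples no route into any table. Yet the definition of a positive participant and the on-study incidence both look across all samples. A programmer has to choose between the two, and the SAP does not say which prevails.

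The samples in question are not a random subset. The SAP's own example is one taken because of an SAE, and pre-rescue samples come from participants whose glycaemic control has failed. These are participants in whom an antibody effect on safety or efficacy would be looked for. If their positive results reach only a listing, treatment-emergent incidence is too low, and the participants concerned sit with the negatives when adverse events and HbA1c change are compared by ADA status.

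**Working it through.** The plan states no ADA incidence and no expected number of unscheduled samples, so there is no planned figure to reproduce. The check is textual, followed by arithmetic on assumed values.

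**1. One participant under the two rules.** Take an efpeglenatide participant who is ADA-negative at baseline and at every scheduled visit, and positive once, at an SAE-driven sample in Week 20.

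| Item | Any-time definition | Listing-only sentence |
|---|---|---|
| In the ADA population (SAP 2.3.3) | yes | yes |
| Counted in treatment-emergent incidence | yes | no |
| Response class (SAP 2.1.5.1) | transient | none |
| Column in the TEAE split (SAP 2.4.5.1) | positive | negative |

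A participant whose only post-baseline sample is unscheduled is a sharper case: that sample admits the participant to the denominator, but its result cannot enter the numerator.

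**2. When a scheduled sample would not make up for it.** ADA is scheduled at Weeks 0, 4, 12, 30 and 56, and 6 weeks after the last dose (about Week 62 for a completer). The gaps are 4 − 0 = 4, 12 − 4 = 8, 30 − 12 = 18, 56 − 30 = 26 and 62 − 56 = 6 weeks. A lasting response is caught at the next scheduled sample; a short one may not be.

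Assume a positive spell of w weeks with onset uniform over Weeks 0 to 56 and every scheduled sample taken. The chance that it misses all scheduled samples through Week 56 is the sum of max(0, gap − w) over the gaps 4, 8, 18 and 26, divided by 56:

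- w = 2: (2 + 6 + 16 + 24)/56 = 48/56 = 86%
- w = 4: (0 + 4 + 14 + 22)/56 = 40/56 = 71%
- w = 8: (0 + 0 + 10 + 18)/56 = 28/56 = 50%
- w = 16: (0 + 0 + 2 + 10)/56 = 12/56 = 21%

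This is the chance that a spell falls between scheduled samples. It is not a misclassification rate, since an unscheduled sample must also fall within the spell.

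**3. Effect on tabulated incidence.** Let k participants be positive only at an unscheduled sample, in an arm of 100 (the planned size, taken as the denominator). Tabulated incidence is true incidence − k/100; the relative loss is k divided by the true number of positives.

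| True incidence | k = 1 | k = 2 | k = 5 |
|---|---|---|---|
| 5% | 4% (loss 20%) | 3% (40%) | 0% (100%) |
| 10% | 9% (10%) | 8% (20%) | 5% (50%) |
| 20% | 19% (5%) | 18% (10%) | 15% (25%) |
| 40% | 39% (2.5%) | 38% (5%) | 35% (12.5%) |

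Both the true incidence and k are assumptions.

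**The case against.** *Summary may mean by-visit summary.* Most of the ADA tables in SAP 2.4.5.9 are by visit, and the any-time definition would still make an SAE-driven positive count. That may well be the intent. It also means the exclusion cannot be taken alone: a reader might infer that these participants will certainly be tabulated as negative in every ADA table, and the definition in the same section does not support that. But the intent is not written. The incidence table is not by visit, and SAP 2.5.5 shows that the authors state a by-visit limit when they mean one.

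*Event-triggered samples distort in the other direction.* They exist because an event occurred, so counting them gives participants with events extra chances to test positive and can inflate an association between ADA and adverse events. Using scheduled samples only equalises ascertainment. This stands. A reader might infer that the exclusion simply biases the ADA-safety association toward none; the direction is in fact a trade-off. The SAP 2.5.5 rule is a good model for participant-level incidence, but it serves abnormality flags, which are outcomes, whereas here ADA status is a grouping variable. This is a reason for a companion table. It does not justify leaving the contradiction in place.

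*Little depends on it.* The ADA analyses are descriptive, the excluded values are still listed, and severe allergic, injection-site and immune complex reactions are summarised by arm whatever the ADA status. All of this stands and limits the weight of the point.

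**Conclusion.** The contradiction is real and should be resolved before the ADA tables are programmed. Under the literal reading, a participant positive only at an SAE-driven or pre-rescue sample is kept in the denominator, is not counted as positive, and is misplaced in the ADA-status splits. The effect is confined to transient positives and to participants with no later scheduled sample. It concerns the efpeglenatide arms only, because ADA summaries are limited to participants treated with efpeglenatide. No primary or secondary efficacy result is affected. The documents do not show how many participants, if any, would be reclassified; the figures above only give the scale under stated assumptions.

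Two further inferences are tempting and are not supported:

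- *That early-discontinuation samples are dropped.* SAP 2.5.4 groups the end-of-treatment visit of a premature discontinuer with unscheduled visits, but only in the window rule for efficacy data. No rule maps that visit for ADA. Participants who stop the IMP remain on the visit schedule with later ADA samples, and those leaving altogether should have the Visit 15 procedures, which include ADA (protocol 1.3, footnote a). What is missing is a rule for these samples.
- *That the 4- and 6-month post-treatment samples are lost to the same effect.* They are requested only from participants who are ADA-positive at the end of the study and had a severe injection-site or hypersensitivity reaction (protocol 8.8.1). Omitting them would not ordinarily turn a positive participant negative, and SAP 2.1.5.1 already includes the post-study period in the persistent-response definition.

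**What to change.** Replace the closing sentence of SAP 2.4.5.9 with text to this effect: *Unscheduled ADA results are left out of by-visit ADA summaries only. Every valid post-baseline sample, including unscheduled, pre-rescue and early end-of-treatment samples, counts toward participant-level treatment-induced and treatment-boosted status, on-study treatment-emergent incidence, and the persistent, transient and indeterminate classes.* Add one line saying how early end-of-treatment ADA samples map to visits in the by-visit tables.

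For TEAEs by ADA status, use this participant-level status and repeat the table with status derived from scheduled samples only. The pair shows whether any association rests on event-triggered sampling.

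The cost is a few lines of SAP text, a change to the derivation code and one extra descriptive table. The results are already destined for the listing, so no new data are needed. The small downside is the unequal ascertainment described above, which the companion table makes visible.
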